**LAY SUMMARY**

This study is intended to improve communication of colposcopy results and follow-up recommendations to patients. Current practice involves results being forwarded from the colposcopy clinic to the family/referring physician who then informs the patient. We are testing an intervention informed by focus groups in which a trained colposcopy nurse (patient liaison) contacts patients directly with their results and follow-up recommendations while providing education and support. We will examine whether this intervention improves patient satisfaction, reduces anxiety, and improves rates of adherence to follow-up and treatment appointments compared to the current practice.

**SUMMARY**

Cervical cancer is largely preventable with regular Pap smear screening that detects pre-cancerous changes that can be diagnosed and treated with colposcopy. This process is limited by patient adherence to the follow-up and treatment recommendations. Currently at Vancouver General Hospital (VGH), the largest colposcopy clinic in the province, results are forwarded from the colposcopy clinic to the family/referring physician who informs patients of results and recommendations. Inefficiencies, omissions or errors in this step may cause patient dissatisfaction, missed appointments, increased costs, and compromise patient outcomes. The primary objective of this study is to examine whether having a trained colposcopy nurse contact patients directly with their results and follow-up recommendations while providing education and support will improve patient satisfaction and reduce anxiety. The secondary aims are to compare the timeliness of receipt of results, rates of adherence to follow-up and treatment appointments, and potentially long-term clinical outcomes between the control and intervention groups.

The first phase of the study involves patient focus groups that will be interviewed about their experiences in colposcopy and what elements of a patient liaison interaction would be most important to them (REB#H16-01422). This information will inform the development of the patient liaison role and approaches to patient interaction to be utilized in the intervention in the second phase (current proposal). The second phase will entail a randomized controlled trial comparing patient anxiety, satisfaction and adherence to follow-up between a control group (current practice) versus the intervention group exposed to the patient liaison at the VGH Colposcopy Clinic. For the primary aim, a questionnaire containing items pertaining to patient anxiety and satisfaction with their experience of receiving their colposcopy results will be administered both to the intervention and control groups and the mean scores pertaining to anxiety and satisfaction will be compared using two-tailed t-tests. For the secondary aim, a chart review at 6-12 months following the initial colposcopy visit will examine the rates of compliance with the recommended follow-up or treatment visits and histologic diagnoses, and comparisons will be sought between the intervention and control groups using z-score test.

## **BACKGROUND AND SIGNIFICANCE**

Cervical cancer is the second most common cancer in women worldwide (incidence of 529,800 new cases annually), and the third leading cause of cancer death. Given the natural history of cervical cancer, cytologic screening (Pap smears) for precursor neoplastic lesions with referral to colposcopy has significantly reduced the morbidity and mortality associated with invasive cervical carcinoma in jurisdictions with screening programs. However, the effectiveness of screening programs for this largely preventable cancer is limited by default rates from colposcopy, which range from 3-9% for initial appointments and 6-16% for subsequent treatment or follow-up visits. A randomized trial found that 20% of women after a biopsy confirmed diagnosis of CIN (cervical intraepithelial neoplasia) did not attend their recommended treatment appointment. Follow-up rates following initial treatment were also found to be poor in one prospective study in which only 31% of women attended the recommended follow-up colposcopy appointment and only 60% had follow-up at 17 months. Delayed and missed appointments not only expose women to the risk of increased morbidity or disease progression, but they also reduce the efficiency of the colposcopy system for the wider population, thereby increasing costs.

A critical step in the colposcopy pathway is communicating results and recommendations for further treatment or follow-up to patients. Communication delays, breakdowns in communication between specialists and primary care providers, and a lack of understanding by patients regarding the significance of their results and necessity for further intervention or follow-up have all been identified as potential contributors to default from colposcopy. Ethnic minorities and those of low socioeconomic status are known to have lower rates of cancer screening associated with late-stage presentations and increased mortality. These patients are particularly vulnerable to breakdowns in the communication of results and follow-up plans, compounded by cultural and language barriers. A recent qualitative focus group study found that patients value receiving results in a timely fashion from a clinically trained staff member with an understanding of the impact of the test result. Correspondingly, studies have shown that adherence to screening, treatment and follow-up have improved with telephone-based interventions in which trained patient navigators contact patients with appointment reminders, education regarding the rationale for each test, follow-up for abnormal test results and counseling for barriers to attendance. These interventions have also been found to be effective in ethnic or socioeconomic populations at higher risk for non-adherence. Anxiety has been identified as a strong correlate of the colposcopy process, and is found to be elevated before, during, and after clinic procedures and may negatively impact adherence to recommendations. There is evidence that providing patients simple (rather than complex) information significantly decreases their anxiety associated with colposcopy.

In our setting, the Vancouver General Hospital (VGH) Colposcopy Clinic is the largest of its kind in British Columbia, comprised of seven clinics per week attended by ten physician specialists who see 15-20 patients per clinic for diagnostic and treatment services. Following a clinic visit, a colposcopy report with results and recommendations is issued to the patient's family/referring physician, typically within 2-3 weeks. It is the responsibility of the individual patient to follow-up with their provider for the results, or for the family physician/referring provider to initiate contact with the patient. The lack of direct contact between the colposcopy clinic and patients regarding test results or ongoing follow-up limits patient engagement and

increases opportunities for communication breakdown. This has the potential to compromise patient outcomes and patient satisfaction and contributes to inefficiencies in the healthcare system.

In the proposed second phase of this study, we aim to utilize information gathered from phase 1 to inform an intervention where a patient liaison nurse will serve as the link between new patients and the colposcopy clinic by communicating results along with treatment or follow-up recommendations to patients. She would explain the rationale behind recommendations and be available to answer patient questions. If this intervention is demonstrated to improve patient anxiety and satisfaction associated with colposcopy and adherence to follow-up and treatment, these results would then support larger studies and provide evidence to advocate for resources to offer this service to all colposcopy patients at VGH and beyond.

### **HYPOTHESIS AND OUTCOMES**

1. Primary outcome: We hypothesize that the intervention group will have lower mean state anxiety scores as measured by the State Trait Anxiety Inventory (STAI).
2. Primary outcome: We hypothesize that participants in the intervention arm will demonstrate higher:
  - A) Overall satisfaction with their colposcopy experience and interactions with colposcopy healthcare professionals; we anticipate higher patient satisfaction scores as well as positive qualitative themes from open-ended questions in the intervention group (PSQ-18 and VSQ-9 Inventories)
  - B) Satisfaction with the information and education they receive regarding colposcopy, their diagnoses and follow-up recommendations; we anticipate higher scores on questionnaire items that measure these factors in the intervention group (PSQ-18 and VSQ-9 Inventories)
3. Secondary outcome: We hypothesize that patients in the intervention group will receive results sooner.
4. Secondary outcome: We hypothesize that participants in the intervention arm will demonstrate greater:
  - A) Knowledge of their colposcopy diagnosis; we anticipate a higher rate of accuracy between the participant self-reported colposcopy diagnosis and actual diagnosis
  - B) Adherence to treatment and follow-up recommendations; we anticipate higher rates of follow-up/treatment visit attendance in the intervention group

### **STUDY DESIGN AND METHODOLOGY**

This is phase two of a two-part study. The first phase employs qualitative methodology with focus groups. Themes from these focus groups will inform development of the nurse-led patient liaison intervention to be employed in the second phase. The first phase has been reviewed in a separate Ethics application (REB#H16-01422).

This is a randomized controlled trial to compare patients who participate in the patient liaison intervention (intervention group) to those who continue with the current system of results reporting via the family/referring physician (control group). Following recruitment and consent, patients will be randomized to the intervention or control group. The control group will receive the standard of care for colposcopy results reporting via their referring physician. Following their

colposcopy visit, control patients are given a slip of paper reminding them to call their family/referring physician for their colposcopy results in three weeks if they have not yet been contacted. Upon receipt of the final pathology, colposcopy reports are prepared by the colposcopists and forwarded to family/referring physicians typically within 2-3 weeks of the visit. Patients then receive the results of their colposcopy report from their family/referring physician by whatever method of communication preferred by that provider.

The participants randomized to the intervention group will be exposed to the patient liaison in receiving their colposcopy report results and recommendations. Rather than receive results from their referring/family physician, an experienced colposcopy nurse will contact participants once the colposcopists complete the final colposcopy report. The colposcopy report will inform the referring provider that these patients will be informed of the results. The colposcopy nurse will provide an explanation of the colposcopy results and subsequent follow-up or treatment recommendations, be available to answer patient questions (within her scope), offer educational or support resources to patients. She will forward any patient questions beyond her scope to the patient's colposcopist who may then provide answers to the patient liaison or to the patient directly depending on the complexity and nature of the question.

The research coordinator ([name]) will subsequently contact all participants (control and intervention groups) to complete a questionnaire following the communication of their colposcopy report. All participants following consent will be asked to provide their preferred contact method (email, telephone) and whether they prefer to access the questionnaire via an Internet link sent to their email or to complete it verbally via telephone with the research coordinator. Control participants will be contacted within 3-4 weeks of their initial colposcopy visit to permit time for communication of their results from their family/referring physician. Intervention group participants will be contacted once the patient liaison nurse has informed the research coordinator that the results have been communicated to the participant. Reminders to complete the questionnaire will be sent at weekly intervals—twice via email, and a third time via telephone. Patients who fail to complete the questionnaire after three reminders will be considered lost to follow-up.

- 1) The questionnaire will contain the following information and validated scales:
  - (a) Demographics\*
  - (b) Date of colposcopy appointment and date that results were communicated (to measure the time interval in days in which results were received by participants)
  - (c) Method of colposcopy results communication – family/referring MD versus patient liaison (to determine intention to treat versus per protocol)
  - (d) State-Trait Anxiety Inventory (STAI)
  - (e) Health Anxiety Inventory (HAI)
  - (f) Short-Form Patient Satisfaction Questionnaire (PSQ- 18)
  - (g) Patient Satisfaction Survey (VSQ-9)
  - (h) Self-reported colposcopy result and recommendation (to be compared to actual result on file)

\*Demographic information collected will include: Age, highest level of education, current employment, and ethnicity. This information is necessary to understand sample diversity, and generalizability of results.

Secondary aims in the randomized trial will be to assess the effectiveness and clinical impact of the patient liaison intervention by comparing: 1) the interval between generation of colposcopy reports and communication of these results to patients; 2) percentage of patients successfully contacted and number of contact attempts both by the patient liaison nurse and the research coordinator administering the questionnaire; 3) the accuracy of patient's understanding of their colposcopy result, measured by the comparison of self-reported and actual result; and 4) rates of patient compliance with recommended follow-up appointments for treatment or repeat colposcopy. Patient electronic charts will be reviewed in 6-12 months following the initial colposcopy visit to collect data regarding histologic diagnoses, adherence to subsequent follow-up or treatment appointments and number of missed/cancelled appointments.

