## **ANALYSIS**

The mean composite scores will be compared between the intervention and control groups with a significance level  $p<0.05$  specifically looking at:

- 1) Mean patient anxiety (quantified by the STAI state subscale and HAI scale) related to receipt of colposcopy results: The State Trait Anxiety Inventory is an established and widely-used anxiety measure with high internal consistency (Cronbach's  $\alpha = 0.83-0.95$  dependent on the population studied). It contains 20 self-reported items that measure situational or state anxiety, and patients rate their agreement with these statements on a four point Likert scale which are then aggregated for a composite score. Mean composite trait and state anxiety scores will be compared between the two groups using the two-tailed t-test.
- 2) Patient satisfaction with the timing and method of communication of their colposcopy results and satisfaction with the information they received concerning their diagnosis, procedures, or recommended management: these will be quantified by the validated PSQ-18 and VSQ-9 scales which have been previously used in patient satisfaction studies at the VGH Colposcopy Clinic. Mean scores on the subscales will be compared between the two groups using the two-tailed t-test.
- 3) The accuracy of participant understanding of their colposcopy diagnosis following the intervention: for all patients, self-reported colposcopy diagnosis will be compared to the diagnosis in the clinic chart and graded as correct or incorrect. A chi-square analysis will be performed to assess whether there is a significant difference between the two groups.
- 4) Timeliness and rates of communication of patient results: The mean interval in days between generation of colposcopy reports and the communication of the result to the patient as well as the mean percentage of successfully contacted participants will be compared between the two groups using t-tests and z-tests.
- 5) Participant adherence to follow-up: patient electronic charts will be reviewed in 6-12 months following the colposcopy. The proportion of patients who complete the recommended follow-up will be compared between groups using z-test.

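### Controls are surveyed at 3-4 weeks whether or not they have their result, so missing or survey-prompted result dates can make the control arm's time to results look too short

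*Protocol*

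**What the plan says.** All of the following is in the Protocol, under Study Design and Methodology, unless another place is named.

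- **Comparator.** "The control group will receive the standard of care for colposcopy results reporting via their referring physician". That care already contains a prompt: "control patients are given a slip of paper reminding them to call their family/referring physician for their colposcopy results in three weeks", if nobody has contacted them by then. Reports typically go to the physician 2-3 weeks after the visit.
- **Survey trigger, control arm.** The calendar: "Control participants will be contacted within 3-4 weeks of their initial colposcopy visit to permit time for communication of their results".
- **Survey trigger, intervention arm.** An event: the nurse tells the coordinator that the result has been given.
- **Reminders, both arms.** "Reminders to complete the questionnaire will be sent at weekly intervals": two by email, then one by telephone.
- **Content.** The questionnaire asks for the date on which results were communicated (item b), the route (item c), and, as item (h), "Self-reported colposcopy result and recommendation (to be compared to actual result on file".
- **Outcomes (Analysis, items 3 to 5).** Self-reported diagnosis is graded correct or incorrect against the chart. The mean number of days from report generation to communication is compared between arms. Adherence is read from charts at 6-12 months: "The proportion of patients who complete the recommended follow-up will be compared between groups using z-test".
- **SAP.** Secondary outcomes are compared by t-tests if continuous and Fisher's exact tests if categorical. It gives no rule for a participant who had no result when surveyed.

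**The concern.** The Protocol intends the questionnaire to follow communication of the report in both arms. Only the intervention arm's trigger secures this. For controls the coordinator works from the visit date, and nothing in the documents checks that a result has arrived.

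A control still without her result at first contact can go one of two ways. She may answer without it; she then has no communication date and drops out of the planned mean. Or she may wait, obtain the result and then answer; her date is credited to standard of care even if a study contact led her to ask for it. The first route leaves out women who are probably among the slowest, and the second may shorten their interval. Both tend to make standard care look quicker than it is.

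Earlier receipt of results is a stated secondary hypothesis, and the Background says that the trial is meant to support a case for resources. A small or null timeliness difference could be misread if the slowest controls were omitted or hurried along.

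**Working it through.** **The plan's own figure.** The only sample size given is for STAI-state: 2 x (1.960 + 1.282)^2 x (10.6/5.3)^2 = 84.1, rounded up to 85 per group, and 85/0.85 = 100. It reproduces, but has no bearing here. The plan gives no sample size or expected interval for timeliness.

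**Step 1: can a control be uninformed at first contact?** Inputs from the Protocol: report to the physician at about day 14-21; first control contact at about day 21-28. The time left for the physician to reach the patient is between 21 - 21 = 0 and 28 - 14 = 14 days. An uninformed control is therefore foreseeable. The documents do not say how common she is.

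**Step 2: how many contacts?** One first contact plus three weekly reminders is at most 4, at about days 21-28, 28-35, 35-42 and 42-49. Only women who have not completed the questionnaire reach the later ones.

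**Step 3: omission from the mean.** Let u be the share of controls who answer without a date, and D the amount by which their eventual mean interval exceeds that of the others. The full mean is (1 - u) x m + u x (m + D) = m + uD. The planned mean uses dated women only and equals m, so it is too short by uD. With u = 10-30% and D = 14 days (both assumed), that is 0.10 x 14 = 1.4 to 0.30 x 14 = 4.2 days. D need not be large: a woman may be uninformed because her report was late, and the planned clock starts only at the report.

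**Step 4: prompted dates.** Let f be the share of uninformed controls who obtain the result because of the survey, over and above the slip, and s the days saved. The mean shortens by u x f x s. With u = 10-30%, f = 25-50% and s = 14 days (all assumed), that is 0.10 x 0.25 x 14 = 0.35 to 0.30 x 0.50 x 14 = 2.1 days. A given woman falls under Step 3 or Step 4, not both, so the two maxima must not be added.

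**Step 5: knowledge.** Assume that 80% are correct if informed and 0% if not, with 20% of controls uninformed when surveyed and the whole intervention arm informed. If all of those controls answer uninformed, the control figure is 0.80 x 0.80 = 64%, a gap of 16 points. If 25% or 50% of them obtain the result first, it is 0.80 x (1 - 0.20 x 0.75) = 68% or 0.80 x (1 - 0.20 x 0.50) = 72%, a gap of 12 or 8 points. Surveying uninformed women widens the gap and prompting them narrows it, so the net direction is open.

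**The case against.** The strongest reply is that standard care already tells an uninformed control, at three weeks, to ring her physician. The first study contact comes in the same week or the next, so only its increment over the slip matters, and that may be small. This stands, and it limits Step 4. It does not touch Step 3, which needs no prompting at all.

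A reader might infer that the survey prompts controls alone and so shrinks the timeliness, knowledge and adherence differences. The documents do not support that.

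- They give no share of uninformed controls and do not reproduce the reminder wording or the full questionnaire, so prompting is possible but not shown. A not-yet-received option may even exist already.
- For adherence, the reminders and the question about the recommendation go to both arms, so the exposure is not confined to controls.
- The Background's remark that "adherence to screening, treatment and follow-up have improved with telephone-based interventions" goes on to describe trained navigators who give education and counselling. It is not evidence that a survey invitation changes attendance.
- A calculation in which the adherence difference vanishes would have to assume that survey contacts work as well as the nurse.
- Adherence is weakly powered in any case. Take 16% default in controls, the top of the Background's range for subsequent visits, and an assumed 8% under the liaison, with 100 per arm. The pooled SE is sqrt(2 x 0.12 x 0.88/100) = 0.0460 and the unpooled SE is sqrt((0.16 x 0.84 + 0.08 x 0.92)/100) = 0.0456. Then (0.08 - 1.96 x 0.0460)/0.0456 = -0.22, which is about 41% power before any dilution.

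The event trigger also has a gap of its own. Intervention participants whom the nurse never reaches have no trigger for the survey and no nurse-communicated date. Leaving them out would flatter the intervention arm, so the direction given here is that of the control-arm problem alone.

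**Conclusion.** The concern holds for timeliness. The survey triggers differ by arm, nothing checks that a control has her result, and neither document says how an undated or late-dated control enters the mean interval. Both routes can shorten the apparent control interval and so bias the comparison towards no difference.

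The size is unknown. On the assumptions in the working it is 0.35 to 2.1 days from prompting, or 1.4 to 4.2 days if all uninformed controls answered without a date. These figures show the scale only. For adherence an effect is possible but not demonstrated, and for knowledge the direction is unsettled. The point concerns secondary outcomes and leaves the STAI-state sample size untouched.

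**What to change.** 1. **Record.** Add a response for results not yet received to item (b), inside the existing questionnaire, and log the date of the coordinator's first contact for every participant. Do not add a separate question before the questionnaire: it would be a more direct prompt than the survey itself.
2. **Analyse timeliness as time to event.** Start at report generation (date from the clinic record), end at communication, and present the cumulative proportion informed by arm. Keep a participant without a result in the analysis, censored at questionnaire completion or at the last contact at which she was known to have none. Apply the same rule to intervention participants not reached, using the nurse's last attempt. Count non-responders of unknown status separately. As a sensitivity analysis, censor at first study contact any result first obtained after it. This should not be the main rule, because it would also discard results that the slip produced.
3. **Report** by arm the share without a result at first contact, and repeat the knowledge comparison with and without those participants. Do not reclassify women informed by their physician: that is their assigned route.
4. **Word the adherence conclusion** as a comparison with standard of care plus study survey contacts, as a limitation, without claiming how large any dilution is.

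The cost is one response option, one date and a little SAP work. Timeliness in uninformed controls is then observed only to the end of survey contact, and censoring at completion may be informative if women wait for the result before answering; the sensitivity analysis addresses this.

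The SAP is dated 30 March 2020 and written in the past tense, so data collection may be over. In that case, compare reported communication dates with first-contact dates where these were kept. The Protocol plans to compare the number of contact attempts but does not say that their dates are recorded. The wording change in item 4 applies either way.

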## **SAMPLE SIZE CALCULATION**

To achieve 90% power for a difference of 5.3 (half of a standard deviation is considered clinically significant) in mean anxiety scores (state subscale of the STAI) between the control and intervention groups with an assumed pooled standard deviation of 10.6 and alpha of 0.05, the required sample size is 85 per group. Accounting for about 15% loss to follow-up, we aim to recruit 100 per group with 200 participants in total. With an estimate of 50% participation, the research nurse will need to attempt to recruit approximately 400 patients to reach this target.

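### Intervention participants are invited to the STAI-state questionnaire only after the nurse reports success, controls by calendar; no invitation is stated for those never reached

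*Protocol*

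**What the plan says.** All of the following is in the protocol's Study Design and Methodology section unless stated.

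- **General statement.** The coordinator is to contact everyone in both groups "to complete a questionnaire following the communication of their colposcopy report".
- **Control trigger.** "Control participants will be contacted within 3-4 weeks of their initial colposcopy visit to permit time for communication of their results". This is a calendar rule.
- **Intervention trigger.** "Intervention group participants will be contacted once the patient liaison nurse has informed the research coordinator that the results have been communicated to the participant". This is an event rule. No latest date is given, and nothing is said about a participant whom the nurse does not reach.
- **Loss to follow-up.** It is defined as non-completion after three reminders, so it describes people who were invited.
- **Questionnaire item (c).** It records the route by which results came, "family/referring MD versus patient liaison (to determine intention to treat versus per protocol").
- **Report timing.** Reports are "forwarded to family/referring physicians typically within 2-3 weeks of the visit". Controls are told to "call their family/referring physician for their colposcopy results in three weeks if they have not yet been contacted".
- **Planned contact data.** A secondary aim compares "percentage of patients successfully contacted and number of contact attempts both by the patient liaison nurse and the research coordinator". Item 4 of the Analysis section compares the report-to-communication interval and the percentage contacted by arm.

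The SAP compares STAI-state with a t-test and adds a regression on trait score and diagnosis severity. It compares survey completers with non-completers, without saying that this is done by arm.

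**The concern.** The Analysis section describes the anxiety outcome as relating to receipt of results, and the main comparison is a plain t-test between arms. For that comparison to reflect randomisation alone, who is measured and when should not depend on what happens after randomisation in one arm only.

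Under the written rules, an intervention participant enters the outcome data only if the nurse succeeds. A control is invited whether or not the physician has succeeded. Two consequences follow:

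1. **Who is measured.** Unreached intervention participants may have no STAI-state score, while the corresponding controls are invited.
2. **When it is measured.** Time since visit, and time since results, can differ between arms.

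The satisfaction scales are in the same questionnaire and share the problem. The Early Stoppage section shows that non-contact was foreseen, but it does not say whether unreached people receive the questionnaire.

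**Working it through.** **1. The plan's own figure.** From the Sample Size Calculation: difference 5.3, SD 10.6, two-sided alpha 0.05, power 90%.

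n = 2 × (1.960 + 1.282)² × (10.6/5.3)² = 84.06, rounded up to 85 per group. Then 85/(1 − 0.15) = 100. Both stated figures reproduce. The standard error is 10.6 × √(2/85) = 1.626, and noncentral-t power at 85 per group is 0.900. The sample size is not in question.

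**2. Timing of the invitation.** Reports are typically ready at day 14-21, and controls are invited at day 21-28. Let L be the days from report to nurse call (assumed; the documents give none). Control minus intervention invitation day runs from 21 − (21 + L) = −L to 28 − (14 + L) = 14 − L.

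| L (assumed) | Gap in days |
|---|---|
| 0 | 0 to +14 |
| 7 | −7 to +7 |
| 14 | −14 to 0 |

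The sign is not fixed. These are invitation days; weekly reminders spread completion further in both arms. The documents give no way to convert days into STAI points.

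**3. Missing invitation (illustration only).** The inputs are assumptions:

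- u, the share of the intervention arm never reached: 5% or 14%. The upper value lies just under the 15% level in Early Stoppage. That rule is one interim look at which the study could be stopped, so it does not cap non-contact.
- d, how far the unreached differ on STAI-state: 5.3 or 10.6 points (0.5 or 1 SD).
- r, the share of the unreached who would have answered the coordinator: one half, with one quarter as a lower case.
- Everyone reached answers, and control loss is unrelated to anxiety.

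Weight of the omitted people: w = ur/(ur + 1 − u). Shift in the intervention mean = w × d.

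| r | u | w | Shift, d = 5.3 | Shift, d = 10.6 |
|---|---|---|---|---|
| 0.5 | 0.05 | 0.025/0.975 = 0.0256 | 0.14 | 0.27 |
| 0.5 | 0.14 | 0.070/0.930 = 0.0753 | 0.40 | 0.80 |
| 0.25 | 0.05 | 0.0125/0.9625 = 0.0130 | 0.07 | 0.14 |
| 0.25 | 0.14 | 0.035/0.895 = 0.0391 | 0.21 | 0.41 |

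At r = 0.5 the shift is 0.14/5.3 = 3% to 0.80/5.3 = 15% of the target difference. With 85 per group (14% fits within the 15% loss allowance):

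- with no true effect, two-sided rejection is 5.1% to 7.8% instead of 5%;
- with a true difference of 5.3 and a shift that attenuates it, power is 88% to 79% instead of 90%.

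For a benefit of the intervention, false benefit and attenuation need opposite signs of d, so they are alternatives and not joint effects. If controls lose a similar share of similar people, the net shift tends to zero.

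**4. Whether the analysis plan covers it.** Analysis item 4 concerns when results were communicated, not when the questionnaire was answered. The SAP regression has no timing term and cannot restore people without a score. The completer comparison would reveal differential loss only if split by arm.

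**The case against.** The strongest reply has four parts.

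- **The triggers have a practical basis.** The nurse can tell the coordinator that results were given. No equivalent report back from family physicians is described, so a calendar proxy is used for controls, expressly to allow time for results to arrive. Both rules aim at the same post-result moment. This stands, and it is a reason to keep both triggers.
- **Earlier results are a hypothesised effect.** Part of any timing difference therefore belongs to the treatment contrast. This also stands. A reader might infer that higher anxiety among controls still waiting is bias; the documents do not support that, because it may be a real effect of usual result delivery.
- **Universal follow-up was intended.** The section says all participants are contacted, item (c) anticipates an intention-to-treat classification, and the Risks section says the referring physician still receives the results. A reader might infer that the plan excludes unreached participants. It does not say so: the operational rule is incomplete, and the stated intention supports completing it.
- **Contact is already compared by arm.** This is true and useful, but contact is not questionnaire completion. The comparison does not show who lacks a STAI-state score or when the others answered.

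A single calendar deadline for everyone may look like the natural cure. It would be a poor trade. If nurse calls come some time after the report, many intervention participants could answer before the call, although the protocol places the questionnaire after communication.

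**Conclusion.** The point holds as a gap in the invitation rule that the analysis plan does not close. As written, measurement of STAI-state depends on a post-randomisation event in the intervention arm only, and time since visit can differ by arm.

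A reader might go further and infer that the rule favours the intervention, or that the t-test result is invalid. The documents support neither. They give no non-contact rate, no anxiety by receipt status and no call lag, and the timing gap can take either sign. The illustrated shift of 0.14-0.80 points rests wholly on assumed inputs, including non-informative control loss, and tends to zero if controls lose similar people. It is modest against 5.3 points. The case for action is that the repair is cheap and affects who enters the primary comparison. It should be fixed; confidence is medium.

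**What to change.** **If data are still being collected.** Keep the existing triggers. Add to Study Design and Methodology that any intervention participant whom the nurse has not reached by the end of the 3-4 week window already used for controls is sent the questionnaire, with the same reminders, and is analysed in the arm as randomised. Add a 'results not yet received' option to items (b), (c) and (h).

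The cost is revised wording, one response option and tracking of visit dates in the intervention arm, with no extra patients or visits. The downside should be stated: these participants answer before having results, as some controls may, and time since results stays unaligned. They should be few if calls follow reports within about a week (day 21 + 7 = day 28). With an assumed 14-day lag, calls would fall at day 28-35 and the fallback would apply to many more, so the call lag should be checked first.

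**If data collection is complete**, as the SAP's past tense suggests, report by arm:

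- numbers unreached and not surveyed;
- numbers surveyed before having results;
- visit-to-questionnaire and result-to-questionnaire intervals;
- the SAP's completer/non-completer comparison.

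Add a STAI-state sensitivity analysis for missing unreached participants and for questionnaire timing, noting that timing is post-randomisation, and qualify the conclusion accordingly. Visit and result dates are item (b), and contact success is already planned. Completion dates should be recoverable from the REDCap audit trail, though the Data Storage section describes it only in general terms. The cost is some tabulation and one added analysis.
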